8.0 End of Study/Early Withdrawal

Standard History and Physical examination including weight will be documented. Laboratory studies will include a CBC with differential, and platelet count.

9.0 Criteria for Response

9.1 Response

All patients who receive one dose of study drugs under this protocol will be evaluable for toxicity. All patients randomized will be considered evaluable for response in the intent-to-treat analysis.

Efficacy assessments will include:

- Hemoglobin, TSAT, and other iron panel test measures
- Patient reported outcomes questionnaires (FACT-Fatigue)
- The use (or lack of use) of other therapies for anemia (eg, RBC or whole blood transfusions, ESA, or both)

9.2 Response will be defined as proportion of achieving an increase in hemoglobin at any time from baseline to end of 3 months, as described below:

Complete response (CR): increase in HGB ≥ 2.0 g/dL above baseline, and/ or
transfusion free.

Partial response (PR): increase in HGB (≥ 1 g/dL- 2 g/dL) above baseline

Minor response (MR): increase in HGB (≥ 0.5 g/dL- 1 g/dL) above baseline

9.3 Toxicity: Toxicities will be graded using the Common Terminology Criteria for Adverse Events v4.03 – CTCAE (see Appendix C). Uncomplicated, severe, or life threatening neutropenia and thrombocytopenia are expected toxicities of the systemic therapy and as such will not be collected as adverse events in this study since the data is already captured through the CORe.

10.0 Criteria for Discontinuation from Treatment

Patients may be discontinued from study treatment at any time. Specific reasons for discontinuing treatment include the following:

- Serious or life-threatening adverse event
- Risk to patients as judged by the Investigator and/or Sponsor
- Severe noncompliance with protocol as defined by not receiving at least 70% of the planned treatment (judged by the Investigator and/or Sponsor).
- Request of the patient
- Patient becomes pregnant
- Progressive disease
- Investigator becomes aware of conditions or events that suggest a possible hazard to patients if the clinical study continues

10.1 Discontinuation from Study

Patients who discontinue from treatment will continue to receive follow-up assessments as part of the study unless they are discontinued from study by one of the following events:

- Withdrawal of consent
- Loss to follow-up
- Death from any cause
- Termination of the study

11.0 Statistical Consideration and Sample Size

Statistical Considerations and Analysis

This study will assess the efficacy of IV Injectafer in improving HGB level in GIST patients planned to receive or receiving systemic therapy and presenting with anemia.

Design and Sample Size/Power

This is a randomized, open label, 2-arm trial of 2-dose IV Injectafer in patients with GIST planned to receive or receiving systemic therapy and presenting with anemia. Arm A patients will receive 2 doses of IV Injectafer over 15 min infusion (prior to start systemic therapy and another same dose 1 week later). Arm B patients will receive oral iron supplement (such as Ferrosequels BID, or ferrous sulphate TID) for 3 months. The primary objective is to evaluate the efficacy of IV Injectafer in patients with GIST planned to receive or receiving systemic therapy and presenting with anemia as compared to the effect of oral iron supplement.

A patient will be considered as to have a complete response (CR) if his/her HGB level increase ≥ 2 g/dL from baseline to any time during 3 months following initiation of the study drug, and/or transfusion free. The primary endpoint is CR rate in 3 months. A total of 50 patients, 25 in each arm, will provide the study 93% power to detect the differences of response between the two arms using a Chi-square test with a 0.05 two-sided significance level when the respective CR rates are 75% (6/8) and 28.6% (8/28) in Arm A, and B (according to our clinical experience). All patients who are randomized will be evaluable for response in the intent-to-treat analysis. nQuery 7.0 was used for the sample size or power calculation.

Analysis Plans

Patients' demographic and clinical characteristics at baseline will be summarized using descriptive statistics such as mean, standard deviation, median, interquartile range (IQR), frequency where appropriate. We will apply Student t-test/Wilcoxon test and Kruskal-Wallis test/ANOVA to compare continuous variables between different patient group, and the chi-square test or the Fisher's exact test to assess the association between two categorical variables [25].

For the analysis of the primary endpoint, Chi-square test will be used to test the difference of CR rates between the two arms. CR rates along with their 95% confidence intervals (CIs) will be estimated by study arm. We will use logistic regression model [26] to assess the effect of patient specific covariates, such as treatment group, gender, etc. on the complete response.

Toxicity data will be summarized by frequency tables for all patients and by treatment arm. For the efficacy endpoint, intent-to-treat analysis will be applied to all randomized patients. For the toxicity endpoint, per-treated analysis will be used to include any patient who received one dose of the treatment regardless of the eligibility nor the duration or dose of the treatment received.

We will analyze patient reported outcomes using standard statistical methods for analyzing continuous data, discrete data, and survival data whenever appropriate. Additional analyses in furtherance of the stated objectives may be conducted as warranted.

Randomization

Stratified randomization will be carried out via CORe. The stratification factor is baseline hemoglobin level <10 g/dL vs ≥10 g/dL.

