2.5 Rationale for the Study

The incidence of anemia in patients with gastrointestinal stromal tumor (GIST) receiving TKIs therapy is high [13]. Anemia in GIST patients can be multifactorial such as: anemia of chronic disease, primary therapy, surgery, blood loss and Iron/vitamin deficiency [6].

In our experience, GIST patients with anemia and IDA do response to oral iron if they can tolerate it. In our observations in patients with GIST on iron therapy, approximately 29% of patients tolerated and had response to oral iron vs 75% had response to IV iron such as iron sucrose. This experience is similar to response rate (73%-77%) reported with iv iron in clinical trials in cancer patients receiving chemotherapy [27]. However, the GIST patients seem to have lower tolerance to oral iron due to the underlying disease and treatment with TKIs. This can explain lower success rate (~29%) in our experience as compared to ~45% reported in clinical trials to oral drugs in cancer patients receiving chemotherapy. Also, multiple infusions of iron sucrose are needed to deliver the total dose of iron. Patients with GIST often present with IDA and anemia often worsens during therapy with TKIs like Gleevec [14]. These patients often have nausea from their systemic therapy and not all patients tolerate oral iron well. Also there is a time lag for response to oral iron. Injectafer is a newly approved, non-dextran IV iron that can be administered in a large dose of 2 infusions 1 week apart (15 mg/kg for a maximum single dose of 750 mg, a total of up to 1500 mg). The safety profile is excellent and has been found effective in correcting IDA. Based on these observations, we are proposing a clinical trial of IV injectafer vs oral iron (to avoid patient selection bias) in GIST patients with IDA planning to start or have recently started systemic therapy to evaluate efficacy and safety with IV injectafer.

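### The primary endpoint, complete response, is defined with 'and/or transfusion free', so it has no single meaning; read literally, an untransfused patient with no hemoglobin rise is a complete responder

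*Combined protocol and SAP*

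**What the plan says.** The primary endpoint is the CR rate in 3 months, compared between arms by a chi-square test in all randomized patients (section 11.0). CR is defined twice:

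- Section 11.0, Design and Sample Size/Power: "HGB level increase ≥ 2 g/dL from baseline to any time during 3 months following initiation of the study drug, and/or transfusion free".
- Section 9.2: "increase in HGB ≥ 2.0 g/dL above baseline, and/ or", with the words 'transfusion free' on the next line.

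The surrounding text points to hemoglobin. Section 9.2 opens with "Response will be defined as proportion of achieving an increase in hemoglobin at any time from baseline to end of 3 months", and section 11.0 opens with "This study will assess the efficacy of IV Injectafer in improving HGB level in GIST patients". The lower grades rest on hemoglobin only, for example "Partial response (PR): increase in HGB (≥ 1 g/dL- 2 g/dL) above baseline".

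Transfusion appears in one other efficacy item, the section 9.1 list, as "The use (or lack of use) of other therapies for anemia", with no link to CR. Section 13.1 treats anemia as an end point when it needs intervention, again with no link to CR.

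The sample size rests on 25 patients per arm and 93% power "when the respective CR rates are 75% (6/8) and 28.6% (8/28) in Arm A, and B (according to our clinical experience"). Section 2.5 describes the same experience as "approximately 29% of patients tolerated and had response to oral iron vs 75% had response to IV iron such as iron sucrose". It gives neither a hemoglobin threshold nor transfusion status.

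**The concern.** 'And/or' admits at least three binary endpoints: the rise alone, the rise together with no transfusion, and either one. They classify the same patient differently. Under 'either one', a patient with no rise and no transfusion is a CR. So is every untransfused patient who meets the partial or minor response criteria, so the grades in section 9.2 are no longer mutually exclusive. A 2 g/dL rise that follows a transfusion is a CR under 'either', is not under 'both' if that transfusion counts, and under 'rise alone' depends on a rule that is not written. No time window is attached to 'transfusion free'.

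This is the only primary endpoint of an open-label trial. If the text stays as it is, the reading could be settled after the data are seen. Under the literal reading the test would mainly compare transfusion use, or the way Arm B patients who stop oral iron are classed, and not hemoglobin response.

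**Working it through.** **Inputs.** From section 11.0: n = 25 per arm, chi-square test, two-sided 0.05, CR rates p_A = 6/8 = 0.75 and p_B = 8/28 = 0.2857. The document gives no transfusion or intolerance rate, so the values of t, m and f below are assumptions shown over a range. In every scenario 75% and 28.6% are taken as the rates of a 2 g/dL rise.

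**The plan's own figure.** Pooled normal formula, with p̄ = (0.75 + 0.2857)/2 = 0.5179:

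power = Φ{[0.4643·√25 − 1.96·√(2·0.5179·0.4821)] / √(0.75·0.25 + 0.2857·0.7143)}
= Φ{(2.3214 − 1.3850)/0.6258} = Φ(1.496) = 93.3%.

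This reproduces the stated 93%. Exact power of the uncorrected chi-square test, summing over both binomials, is 94.5%. Powers below are exact unless marked otherwise.

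**Reading 1, rise alone.** 75% versus 28.6%; power 94.5%.

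**Reading 2, rise or transfusion free.** Let t be the share of non-risers who are transfused, the same in both arms, with everyone assessed. A patient then fails only by having no rise and being transfused, so CR_A = 1 − 0.25t and CR_B = 1 − 0.7143t.

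| t | CR A | CR B | Power |
|---|---|---|---|
| 10% | 97.5% | 92.9% | 6% |
| 20% | 95.0% | 85.7% | 19% |
| 30% | 92.5% | 78.6% | 30% |
| 50% | 87.5% | 64.3% | 51% |

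Now let a share m of Arm B, all non-risers, count as non-CR for intolerance or missing data. CR_B becomes 1 − m − (0.7143 − m)t, with CR_A unchanged.

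| m | Power over t = 10% to 50% |
|---|---|
| 10% | 39% to 65% |
| 20% | 72% to 77% |
| 30% | 87% to 91% |
| 40% | 93% to 98% |

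**Does 'or' fit the planning rate?** For Arm B to have a 28.6% CR rate under 'or', the share transfused without a 2 g/dL rise must be 0.7143 − m:

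- m = 0: 71.4%, or 17.9 of 25 patients
- m = 20%: 51.4%, or 12.9 of 25
- m = 40%: 31.4%, or 7.9 of 25

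Section 4.0 admits patients with hemoglobin of 8 to 11 g/dL and excludes overt bleeding. The first of these shares is therefore hard to reconcile with a planned 28.6%. This is inference, because the document gives no transfusion rate.

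**Reading 3, rise and transfusion free.** Let f be the share of risers who are transfusion free, so CR = f × the rise rate.

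| f in A | f in B | CR A | CR B | Exact | Approx. |
|---|---|---|---|---|---|
| 95% | 95% | 71.3% | 27.1% | 92% | 90.2% |
| 90% | 90% | 67.5% | 25.7% | 89% | 86.5% |
| 80% | 80% | 60.0% | 22.9% | 81% | 77.7% |
| 95% | 80% | 71.3% | 22.9% | 96% | 95.3% |
| 80% | 95% | 60.0% | 27.1% | 70% | 65.8% |

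**The case against.** The best defence is that the intent can be recovered. Section 9.2 introduces the grades as increases in hemoglobin, section 11.0 speaks of improving hemoglobin, and the partial and minor grades would be nearly empty under 'or'. On that view the real dispute is only rise alone against rise without transfusion. There the effect on power is modest: none for the first, and 92% to 81% for the second at equal shares. The 70% case needs more transfusion among risers on IV iron than on oral iron, which nothing in the document suggests; section 2.1 cites IV iron as reducing transfusion. The 'or' powers rest on assumed rates. The scenarios with Arm B patients counted as failures bring in a separate question. Section 10.1 keeps patients who discontinue treatment in follow-up and section 7.0 schedules weekly blood counts, so stopping oral iron need not mean missing hemoglobin.

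Most of this stands as a limit on the numbers, which are illustrations. It does not remove the defect. The opening sentence of section 9.2 hands the definition to the line that contains 'and/or', and section 11.0 repeats that wording, so neither section corrects the other. Even a hemoglobin-based reading leaves two different endpoints and no rule for readings taken after a transfusion. Section 5.3 lets Arm B patients who cannot tolerate oral iron come off protocol, the intent-to-treat analysis keeps them, and no rule says how they are classed.

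**Conclusion.** The concern holds, and the primary endpoint must be fixed before analysis. It is wrong as written: one permitted reading makes a complete responder of a patient whose hemoglobin never rises, and no other text excludes it. Context favours a hemoglobin-based reading, but the rule does not say so.

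The 93% power is arithmetically right and stands under the rise-alone reading, provided 75% and 28.6% are rates of a 2 g/dL rise. Under 'and' it may fall or rise with transfusion use by arm (70% to 96% in the cases shown). Under 'or' it ranges from 6% to 98%, depending on assumed transfusion and on how off-protocol Arm B patients are classed. The conclusion rests on the wording; the power figures show only how much depends on it.

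**What to change.** Before analysis, delete 'and/or' and put one hemoglobin-based CR definition, in the same words, in sections 9.2 and 11.0. The sponsor chooses between:

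1. a rise of at least 2.0 g/dL within 3 months of starting study drug, with a stated rule for hemoglobin readings after a transfusion; or
2. the same rise with no red-cell or whole-blood transfusion, with the window stated as either up to the qualifying reading or the full 3 months.

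With either choice:

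- State how randomized patients who come off protocol or lack hemoglobin data are classed.
- Record transfusion dates and report the transfusion-free proportion by arm as a separate secondary endpoint.
- Check whether 6/8 and 8/28 were measured by the chosen definition. If not, restate the expected CR rates and the power on that definition.

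The cost is a wording amendment in two sections, a check of the source records, and a data item: transfusion use is a listed efficacy assessment in section 9.1, but section 7.0 gives it no schedule. Definition 2 may also cost power. If 90% or 80% of risers in both arms are transfusion free, exact power goes from 94.5% to 89% or 81% (93.3% to 86.5% or 77.7% by the approximation behind the stated 93%). It need not fall if the transfusion-free share is higher in Arm A.

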5.0 Treatment Plan

5.1 Study Drug Treatment

This is an open label, randomized, phase II trial. Approximately 50 evaluable subjects will be randomly assigned to arm A and arm B (1:1).

Prior to randomization, all patients will be stratified into < 10g/dL vs. \geq 10g/dL.

Treatment Plan:

Fifty patients with GIST will be randomized 1:1 into two treatment arms; total 25 patients in each of the two arms:

Arm A/ investigational arm: all subjects (n=25) will receive 2 doses of Injectafer® at 15 mg/kg for a maximum single dose of 750 mg, given 7 days apart for a total of up to 1500 mg. The first IV infusion will be given prior to starting systemic therapy. The dose will be repeated 1 week later. It will be diluted in no more than 250 mL of normal saline and infused over 15 minutes.

Arm B/control arm: all patients (n=25) will receive oral iron (dose equivalent of 150-200 mg of elemental iron/day) supplement daily (such as Ferrosequels, BID, or ferrous sulphate, TID) for 3 months. Different iron preparation can be used based on patient's tolerance/preference.

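### Randomization is stratified by baseline Hgb, but the primary test ignores the stratum and no confidence interval for the between-arm difference is planned

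*Combined protocol and SAP*

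**What the plan says.** **Design.** Section 5.1 requires stratification by Hgb before randomization ("Prior to randomization, all patients will be stratified into" two groups, below 10 g/dL and 10 g/dL or above). Section 11.0, Randomization, repeats it: "The stratification factor is baseline hemoglobin level <10 g/dL vs ≥10 g/dL".

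**Primary test.** Section 11.0, Design and Sample Size/Power, bases the 93% power on 25 patients per arm, "using a Chi-square test with a 0.05 two-sided significance level", with CR rates of 75% and 28.6%. Section 11.0, Analysis Plans, uses the same test: "For the analysis of the primary endpoint, Chi-square test will be used to test the difference of CR rates between the two arms". Neither place mentions the stratum.

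**Estimation.** "CR rates along with their 95% confidence intervals (CIs) will be estimated by study arm". No section plans an interval for the difference, ratio or odds ratio between arms.

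**Model.** A logistic regression is planned "to assess the effect of patient specific covariates, such as treatment group, gender, etc. on the complete response". This open list neither excludes baseline Hgb nor commits to it.

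**The concern.** A factor chosen to stratify randomization is normally carried into the primary analysis. If it predicts the outcome and the arms are balanced on it, a test that ignores it uses too large a variance and becomes conservative. Here the only design factor is left out of the primary test, and gender, which is not a design factor, is named in the model instead. In an open-label trial the adjusted analysis is better fixed in advance than left to an open list.

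The second issue is estimation. The trial's question is how IV iron compares with oral iron. Two separate arm intervals do not directly state how large or how uncertain that contrast is, and readers often misread their overlap.

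**Working it through.** **Inputs from section 11.0:** 25 per arm; two-sided alpha 0.05; CR 75% (6/8) in Arm A and 8/28 = 28.6% in Arm B.

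**Assumed, because the documents are silent:** the size of the strata, how strongly Hgb predicts CR, and how closely the arms are balanced within strata. Even the direction of an Hgb effect is uncertain, because CR also contains "and/or transfusion free. The primary endpoint is CR rate in 3 months".

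**1. The plan's power.** The mean rate is (0.75 + 0.2857)/2 = 0.5179.
- SE under the null = √(2 × 0.5179 × 0.4821/25) = 0.1413.
- SE under the alternative = √(0.75 × 0.25/25 + 0.2857 × 0.7143/25) = 0.1252.
- Power = Φ[(0.4643 − 1.96 × 0.1413)/0.1252] = Φ(1.496) = 93.3%.

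The stated 93% reproduces, and it rests on the unstratified test.

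**2. Size of the chi-square with no stratum effect.** Exact enumeration of all outcomes at 25/25, without continuity correction, gives 5.36% at a common CR of 28.6%, 5.41% at 75% and 6.49% at 50%. This slight excess comes from discreteness and has nothing to do with stratification.

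**3. Size with a prognostic stratum.** For stratum h, let a be the CRs in Arm A, m the CRs in both arms, n_A and n_B the arm sizes and T = n_A + n_B. The CMH statistic is (Σ[a − m·n_A/T])² / Σ[n_A·n_B·m(T − m)/(T²(T − 1))]. Both tests were enumerated exactly with near-balanced strata: arms 13/12 and 12/13 for equal strata, 8/17 and 7/18 for a 30/70 split.

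| Common CR 50%, stratum odds ratio | 2 | 4 | 9 | 16 |
|---|---|---|---|---|
| Equal strata, chi-square | 6.1% | 5.1% | 3.5% | 2.4% |
| Equal strata, CMH | 4.9% | 4.9% | 4.7% | 4.5% |
| 30/70, chi-square | 6.2% | 5.4% | 4.2% | 3.5% |
| 30/70, CMH | 4.8% | 5.0% | 5.2% | 5.1% |

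At a common CR of 28.6% with equal strata and odds ratios 1/2/4/9/16, the chi-square gives 5.4/5.1/4.4/3.4/2.8% and CMH 4.8 to 5.0%. Odds ratios of 9 and 16 mean stratum CR rates of 25% vs 75% and 20% vs 80%; nothing in the documents supports effects that large. With perfectly balanced strata (13/13 and 12/12) the largest CMH size over CR rates of 10 to 90% is 5.5%. Without balance within strata (400,000 simulated trials per odds ratio, common CR 50%) the conservative shift disappears: the chi-square stays at 6.5% and CMH at 4.8 to 4.9%.

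**4. Power at 75% vs 28.6%.** Over odds ratios 1 to 16, both splits, and the odd patient placed in either arm, the chi-square has 94.2% to about 98% and CMH 92.3 to 98.1%. At odds ratio 1 with equal strata it is 94.5% vs 92.5%. The largest loss for CMH is about 2.6 points: 95.2% vs 92.6% at odds ratio 2, 30/70 split.

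**5. The missing interval.** At the planned rates the difference is 0.464 ± 1.96 × 0.1252, that is 46.4 points with a 95% CI of 21.9 to 71.0. As an illustration of why arm intervals do not replace it, take 17/25 vs 10/25. Chi-square = 50 × (17 × 15 − 10 × 8)²/(25 × 25 × 27 × 23) = 3.945, p = 0.047. The Wilson intervals for the arms are 48 to 83% and 23 to 59%, which overlap. The Newcombe interval for the 28-point difference is 0.5 to 50.2 points.

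**The case against.** The plan is internally consistent: the trial is powered on the unstratified chi-square and analysed with it, and no section promises a stratified analysis. The test does not gain false positives from ignoring the stratum. The highest size, 6.5%, comes from discreteness at a 50% rate; at the plan's rates it is 5.4%. Stratum share, prognostic strength and balance are all assumed. If Hgb is weakly prognostic the chi-square is nominally the more powerful test. The logistic model includes treatment group, so a between-arm odds ratio is foreseeable, and the plan allows additional analyses. The 17/25 vs 10/25 example sits at the edge of significance; at 19/25 vs 7/25, the counts nearest the planned rates, the Wilson intervals (57 to 89% and 14 to 48%) do not overlap. A reader could also compute an unadjusted interval from the reported counts.

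Most of this stands, and it limits the severity. Part of the chi-square's nominal power advantage comes from running slightly above 5%. What the objection does not supply is a commitment: neither the logistic model nor the additional-analyses sentence fixes a stratum-adjusted comparison or a confidence interval for the contrast.

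**Conclusion.** The point holds as a minor improvement to the analysis; the stated sample size and power are not wrong. Depending on a stratum effect that nobody can know in advance, the planned test's size runs from about 2.4% to 6.5% in the scenarios at a common CR of 50%, against 4.5 to 5.2% for CMH. The conservative end requires both balance within strata and an implausibly strong Hgb effect; at weak effects and the plan's own rates the two tests differ by well under one point. The missing interval for the difference depends on none of these assumptions and is the more useful part to correct: at the planned rates it would span about 49 points (71.0 − 21.9), which matters for interpreting a 50-patient phase II trial.

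**What to change.** In section 11.0, Analysis Plans:

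- Make the primary test a CMH test stratified by baseline Hgb (<10 vs ≥10 g/dL).
- Report the stratified difference in CR rates with its 95% CI, and name the interval method.
- Name baseline Hgb alongside treatment in the logistic model.
- Keep the plain chi-square as a sensitivity analysis.

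The power sentence under Design and Sample Size/Power names the chi-square and should be restated to match. N stays at 50. The cost is wording plus at most about 2.6 points of nominal power when the stratum has little effect, leaving about 92 to 93%. If the chi-square is kept as primary, the interval for the difference and the named Hgb covariate should still be added.

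### The supporting logistic model for CR has no small-sample fit and no limit on terms, so at the planning rates its median treatment odds ratio runs about 10–14% high with one covariate and 40–45% high with five

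*Combined protocol and SAP*

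**What the plan says.** Section 11.0, Analysis Plans, makes the chi-square test the primary comparison and reports CR rates with 95% confidence intervals for each arm. It then plans a logistic regression "to assess the effect of patient specific covariates, such as treatment group, gender, etc. on the complete response". The list ends in *etc.*: there is no closed set of covariates, no maximum number and no selection rule. No penalized, exact or otherwise bias-reduced fit is mentioned. The randomization stratum (baseline hemoglobin below 10 versus 10 g/dL or more; sections 5.1 and 11.0, Randomization) is not named as a covariate.

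The sample size paragraph of the same section states "A total of 50 patients, 25 in each arm, will provide the study 93% power". That figure is for a two-sided 5% chi-square comparison, and the assumed effect behind it is given in the clause "when the respective CR rates are 75% (6/8) and 28.6% (8/28) in Arm A, and B". On the analysis set the section says "All patients who are randomized will be evaluable for response in the intent-to-treat analysis".

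**The concern.** Maximum-likelihood estimates in logistic regression are biased away from the null in small samples, and the bias grows with the number of parameters relative to the number of events and non-events. Here about 26 CRs and 24 non-CRs are expected. The model contains treatment, names gender and leaves room for any number of further terms. If it is fitted in the usual way, its treatment odds ratio and its covariate odds ratios will tend to look larger than they are, by an amount that depends on how many terms are added. The plan specifies no risk difference, relative risk or between-arm confidence interval, so a reader who wants a single adjusted treatment effect may turn to this model.

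**Working it through.** **Inputs.** From section 11.0: 25 patients per arm, CR rates 0.75 and 8/28 = 0.2857, two-sided 0.05, all randomized patients analyzed. From section 2.5: an alternative oral-iron response of about 45%, used for sensitivity only. My assumptions, not in the documents: ordinary maximum likelihood; covariates counted in addition to treatment; covariates unrelated to response in the base case; inflation measured as median fitted odds ratio divided by true odds ratio.

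**1. The plan's own figure.** The mean rate is (0.75 + 0.2857)/2 = 0.5179.

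z = [√25 × 0.4643 − 1.96 × √(2 × 0.5179 × 0.4821)] / √(0.75 × 0.25 + 0.2857 × 0.7143) = (2.3214 − 1.3850)/0.6258 = 1.496

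This gives power of 93.3%, so the stated 93% reproduces.

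**2. True odds ratio and expected events.** (0.75/0.25)/(0.2857/0.7143) = 3/0.4 = 7.5. Expected CRs are 25 × 0.75 + 25 × 0.2857 = 25.9, and expected non-CRs 24.1.

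**3. No covariate.** Enumerating all 2×2 tables at the planning rates, the median sample odds ratio is that of 19/25 versus 7/25: (19 × 18)/(6 × 7) = 8.14. The ratio to the truth is 8.14/7.5 = 1.09, so about 9 points of inflation exist before any covariate enters.

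**4. With covariates.** Simulated trials (3,000 to 40,000 per setting; ranges cover different runs and covariate types), maximum likelihood:

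| Covariates added to treatment | Inflation of median, 75% vs 28.6% (true 7.5) | Implied median odds ratio | Inflation of median, 75% vs 45% (true 3.67) |
|---|---|---|---|
| 1 | 10–14% | 8.3–8.6 | 5–9% |
| 2 | 15–18% | 8.6–8.9 | – |
| 5 | 40–45% | 10.5–10.9 | 23–26% |

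The third column is 7.5 multiplied by one plus the inflation. With equal CR rates of 50% in both arms the inflation is nil.

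**5. Sensitivity to the assumptions.**
- When covariates do predict response (log odds ratio 0.3 to 0.5 per SD), inflation against the conditional odds ratio is 11–13% with one and 51–70% with five.
- If *five* is taken to include treatment itself, so four added covariates, the base-case figure is about 34%.
- On the scale of the exponentiated mean log odds ratio, the base-case inflation is 18–19% with one and 57–62% with five.

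**6. What is not harmed.** Coverage of the 95% interval with covariates unrelated to response stayed at 94–96% with up to five. Separation (an infinite estimate) occurred in 0.1% to 1.3% of trials.

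**7. The alternative.** A Firth fit to the same base-case settings keeps the median within about 5% of the true odds ratio with one to five covariates. Its root mean squared error on the log scale is 0.65–0.75, against 0.77–1.24 for maximum likelihood, and its coverage is at least nominal.

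**The case against.** The case against is substantial.

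- *The effect size is available elsewhere.* The documents never name an odds ratio as a result. The primary endpoint is reported through a chi-square test and CR rates by arm, which carry none of this bias. A reader might infer that the published effect of Injectafer over oral iron would be overstated. The documents do not support that: the logistic model is a supporting analysis, and nothing says its odds ratio is the headline. This stands.
- *Covariates are not the whole cause.* A reader might put the entire inflation down to the open list. About 9 points are there with none, so one covariate adds only a few. The list matters mainly when it grows long. This stands.
- *It is a tendency, not a certainty.* With one covariate about 57% of fits exceed the true value, and with five about 67%. A 13% shift is ln 1.13 = 0.12 on the log scale, against a median standard error of 0.68, so about 0.2 standard errors. Intervals still cover. This stands, although a covering interval does not correct a point estimate.
- *The effect may be smaller.* The 75% rests on 6 of 8 patients, and a smaller true effect brings a smaller bias. The percentages must therefore be read as conditional on the planning rates.
- *Five covariates in one model is a construction.* The plan names only treatment and gender, and one-at-a-time models would also fit its wording. That is fair, but nothing in the plan rules out the larger model.
- *Maximum likelihood is conventional in a phase II supporting model.* True, but capping the list at two covariates would still leave 15–18%. A bias-reduced fit does better on bias and on mean squared error.

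**Conclusion.** The point holds as a cheap improvement to a supporting analysis. Fitted by ordinary maximum likelihood in 50 patients, the CR model will tend to overstate the treatment odds ratio if the planning rates are true: modestly with one or two covariates, materially with five. The size rests on those rates, on reading the unspecified fit as maximum likelihood, and on the median as the yardstick. It creates no spurious effect where there is none and does not invalidate the intervals. An unconditional statement that the trial's treatment effect is inflated by 13% or 40% would go beyond the documents, because the primary test and the arm-level results do not depend on this model.

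**What to change.** In section 11.0, Analysis Plans, state that the logistic model for CR will be fitted by Firth penalized likelihood with profile-likelihood 95% confidence intervals. Restrict it to treatment, the hemoglobin stratum (below 10 versus 10 g/dL or more) and at most one further baseline covariate, fixed before data lock. Any other covariate of interest is shown only in its own model, with treatment plus that one covariate.

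The cost is about one sentence, and the method is in standard software. The downside is small: a slightly less favorable odds ratio and fewer covariates in any one model. The primary analysis and the sample size stay as they are.
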